## STUDY PROTOCOL AND STATISTICAL ANALYSES

### Study Population

Our study adhered to the Helsinki Declaration developed by the World Medical Association for medical research involving human material and data. The study protocol was approved by the University of Health Sciences Hamidiye Scientific Research Ethics Committee. Written informed consent was obtained from the participants. The trial was registered at clinicaltrials.gov (NCT04334681). This study retrospectively reviewed the data of 313 patients, older than 18 years, who underwent unroofing curettage (UC) and rhomboid excision and MLF surgeries at Konya Training and Research Hospital between January 2013 and January 2017.

Patients with common gluteal pilonidal disease, collagen tissue disease, and irregular diabetes mellitus were excluded. The data of 278 patients who did not have deficiencies in file and follow-up information were divided into the UC group (n, 135) and rhomboid excision and MLF group (MLF group; n, 143) and analyzed.

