## Postoperative care

Patients who underwent the surgery under local anesthesia were discharged on the same day. Patients on whom spinal anesthesia was used stayed in the hospital for 1 or more days.

Antibiotics were not given to the patients in either group. An analgesic containing diclofenac sodium (50 mg bid) was prescribed, and patients were recommended to take it if they experienced pain.

Dressings were changed in the outpatient clinic for the first 3 days in the UC group. Afterward, the process of dressing was explained to the patient's relatives, and the dressing process was continued at home. We called the patient for follow-up at 7–10-day intervals.

In the MLF group, the wound was checked at 2-day intervals after discharge from the hospital. The surgeon removed the sutures after observing for complete wound epithelization. All patients in either group were followed up for wound complications for 1 month after discharge from the hospital.

Patients were contacted via telephone for follow-up at 6 months and 1 year postoperative. Following this, they were then contacted for an annual check. The patients were questioned regarding their degree of satisfaction with the surgery and the postoperative results (graded as excellent, good, not bad, and bad). Surgeons recorded information on treatment, the healing process, follow-up examinations, readmission, reoperation, and revision on follow-up forms.

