### Statistical analyses

All statistical analyses were conducted using SPSS for Windows, version 22 (IBM Corp, Armonk, NY). Firstly, Kolmogorov–Smirnov and Shapiro–Wilk normality tests were performed. If the normality assumption could not be achieved in any group, nonparametric test methods were chosen. Secondly, the Mann–Whitney U test was performed to compare the obtained variables between groups.

The chi-square and Fisher exact tests were used to analyze the relationships or differences of categorical variables between groups.

Comparative results and other demographic characteristics between groups were presented with the ratio of qualitative variables. Quantitative variables are represented by means. A value of  $p < 0.05$  was considered statistically significant.

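### Readmission, reoperation and revision have no time point; if they are compared by chi-square or Fisher, the result is biased whenever follow-up differs between the two surgical series

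*Combined protocol and SAP*

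**What the plan says.** The Postoperative care section lists what was kept on file: "Surgeons recorded information on treatment, the healing process, follow-up examinations, readmission, reoperation, and revision on follow-up forms". No time window is attached to readmission, reoperation or revision. The only outcome with a fixed window is wound complications: "All patients in either group were followed up for wound complications for 1 month after discharge from the hospital".

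Longer contact was by telephone. The same section says "Patients were contacted via telephone for follow-up at 6 months and 1 year postoperative", and then "Following this, they were then contacted for an annual check". It gives no end to the annual checks, no minimum length of follow-up and no data cut. On what was asked, it says "The patients were questioned regarding their degree of satisfaction with the surgery and the postoperative results"; dates of events are not mentioned.

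Under Study Population, the plan states "This study retrospectively reviewed the data of 313 patients", operated on "between January 2013 and January 2017". The analysis keeps 278 of them whose file and follow-up information was not deficient (135 unroofing curettage, 143 modified Limberg flap). Deficiency is not defined by duration.

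The Statistical analyses section offers normality tests, Mann-Whitney, and for categorical data: "The chi-square and Fisher exact tests were used to analyze the relationships or differences of categorical variables between groups". It does not name the variables, and it has no fixed-time, person-time or censored analysis.

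**The concern.** Readmission, reoperation and revision accumulate with time. A patient operated on early in the accrual period can be observed for longer than one operated on late, and so has more opportunity to record an event. A crude proportion pools these unequal exposures and cannot be read as a risk at any stated time.

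This alone makes the figures hard to interpret. It becomes a bias in the comparison if one group was followed longer than the other, because that group then shows more events even when the underlying hazard is the same. Each group is one surgeon's series (Surgical procedure section), and no randomisation is described, so nothing in the design forces calendar time, and hence follow-up, to balance. Without follow-up length per group, a reader cannot tell whether a difference in reoperation reflects the technique or the time observed.

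**Working it through.** The plan contains no sample-size, power or event-rate figure, so there is no stated result to reproduce. The calculation below shows how large the effect could be.

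**Inputs from the documents.** Group sizes are 135 and 143 (135 + 143 = 278). The significance level is 0.05, taken as two-sided. Operations span 4 years.

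**Inputs assumed.** Event rates and follow-up lengths are assumed. All patients within a group get the same follow-up, and the true hazard is identical in both groups, so every rejection is a false positive.

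**Method.** Exact enumeration of all 136 × 144 possible outcomes, with uncorrected chi-square and two-sided Fisher. The longer follow-up is placed in either group in turn.

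**Scenario A, constant hazard.** Risk by time t is F(t) = 1 − exp(−h·t), with h = 2, 3 and 5% per year. For example, h = 3% gives F(3) = 1 − exp(−0.09) = 8.6%, F(3.5) = 1 − exp(−0.105) = 10.0% and F(4) = 1 − exp(−0.12) = 11.3%.

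**Scenario B, events mostly in year 1.** 8% have an event in year 1, then a rate l of 0.5 or 1% per year: F(t) = 1 − 0.92·exp(−l·(t − 1)). This gives 8.9% v 9.1% (l = 0.5%) and 9.8% v 10.3% (l = 1%) at 3 v 3.5 years. At 3 v 4 years it gives 8.9% v 9.4% and 9.8% v 10.7%.

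| Follow-up, years | A: chi-square | A: Fisher | B: chi-square | B: Fisher |
|---|---|---|---|---|
| 3 v 3 | about 5% | 3.5-4.0% | about 5% | about 3.8% |
| 3 v 3.5 | 6.0-7.9% | 4.5-6.8% | 5.1-5.2% | 3.9-4.1% |
| 3 v 4 | 9.1-15.9% | 7.3-14.3% | 5.2-5.8% | 3.9-4.6% |

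**Accrual imbalance needed for such gaps.** Let a share s of one group and 1 − s of the other be operated on in the first two of the four years, evenly within each half, with a common data cut. Mean operation time is s·1 + (1 − s)·3 = 3 − 2s years in the first group and 1 + 2s in the other. The gap in mean follow-up is therefore 4s − 2 = 2(2s − 1) years. A gap of 0.5 years needs s = 62.5% (62.5% v 37.5%); a gap of 1 year needs s = 75% (75% v 25%).

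**What a 1-year window does.** With both groups cut at 1 year, chi-square rejection is 4.2-5.0% and Fisher 1.7-3.8% across both scenarios, so the inflation is gone. The price is the share of 3-year events that fall after year 1, 1 − F(1)/F(3). In A this is 66.0%, 65.7% and 65.0% for h = 2, 3 and 5%. In B it is 10.3% and 18.5% for l = 0.5 and 1%.

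**The case against.** The strongest case on the other side is that only an unspecified time point is established, not a faulty test. The three outcomes are listed as recorded items; the plan does not say they were tested, and they may have been given as counts. This stands, and it is why the point is conditional.

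A reader might infer from the four-year accrual that the groups differ in follow-up by years. The documents do not support that. The four years are a spread between patients. Both techniques are described for the same hospital and period, with one shared telephone schedule. A spread that is similar in both groups does not bias the comparison; only a difference between the two distributions does.

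A reader might also construct much larger inflation. A normal approximation at 2 v 4 years gives 26-55% rejection at 2-5% per year. Under the accrual formula above, a 2-year gap needs s = 1: one group operated on entirely in the first two years and the other entirely in the last two. Nothing in the documents suggests this.

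Partial safeguards exist. Patients with deficient follow-up information were dropped, and a missed 1-year call could well count as a deficiency, so a shared one-year minimum is plausible. But it is not defined, the outcomes are not tied to it, and later annual calls can go on adding events to some patients and not others.

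Finally, a 1-year window costs most where the bias matters most: under constant hazard it discards about 65% of 3-year events. This also stands, and it is why a censored analysis should come first, with the window as the fallback.

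**Conclusion.** The point holds in conditional form. Readmission, reoperation and revision have no defined time, follow-up has no stated end, and the only categorical methods in the plan ignore time at risk. If the outcomes are compared by those methods, the proportions cannot be read as risks. The comparison is biased if follow-up is distributed differently in the two series. That the comparison is actually biased does not follow from the documents.

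Direction and size are unknown. Under assumed equal constant hazards of 2-5% per year, the chi-square false-positive rate is 6-8% for a 0.5-year gap and 9-16% for a 1-year gap; Fisher is somewhat lower. If events fall mostly in year 1, the rate is at most about 6%, which is negligible. The plan should be changed, with moderate priority, because a better analysis is available and its first step needs only two dates per patient.

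**What to change.** 1. Report the median and range of follow-up per group, from operation and last-contact dates. This shows whether the groups differ.
2. Where event and last-contact dates can be recovered, compare readmission, reoperation and revision by Kaplan-Meier with a log-rank test, censored at last contact. If events are known only to fall between annual calls, use a yearly life table.
3. Otherwise restrict chi-square or Fisher to events within a window completed by every patient compared, for example up to the scheduled 1-year contact, and label the result as 1-year risk. Give later events as descriptive counts beside follow-up length. If events up to that point cannot be confirmed from the files, give counts by group without a test.

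**Cost.** Steps 2 and 3 may need file review for event timing in up to 278 patients, since the plan mentions no event dates. The 1-year fallback omits later events (65-66% of 3-year events under the constant-hazard assumption, 10-19% if front-loaded), and patients without confirmed 1-year data leave that comparison. None of this removes the confounding of technique with surgeon described under Surgical procedure; it deals only with unequal time observed.
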